10. RISK/BENEFIT ASSESSMENT

10.1. Potential Risks

The following risks have been most frequently reported in association to the recombinant zoster vaccine:

- pain (78.0%),
- redness (38.1%),
- swelling (25.9%);
- myalgia (44.7%),
- fatigue (44.5%),
- headache (37.7%),
- shivering (26.8%),
- fever (20.5%),
- and gastrointestinal symptoms (17.3%).

Unsolicited adverse events occurring within 30 days of vaccination were reported in 50.5% of subjects receiving Shingrix. Unsolicited adverse events that occurred in $\geq 1\%$ of recipients of Shingrix and at a rate at least 1.5-fold higher than placebo included the following:

- chills (3.5% versus 0.2%),
- injection site pruritus (2.2% versus 0.2%),
- malaise (1.7% versus 0.3%),
- arthralgia (1.7% versus 1.2%),
- nausea (1.4% versus 0.5%),
- dizziness (1.2% versus 0.8%).

In addition to risks secondary to the vaccine itself, confidentiality breach is a risk associated with the chart review we will need to perform.

Risks associated with venipuncture include vasovagal episodes, ecchymoses at the site of blood removal, and extremely rare instances of infection.

10.2. Protection Against Risks

To minimize risks of discomfort associated to venipuncture and vaccine administration, cold compresses may be applied to the punctured/vaccinated areas as needed.

Should subjects experience an immediate severe adverse effect, they will receive appropriate routine care through personnel at the Cancer Center, which will be covered by patients' insurance.

10.3. Potential Benefits to Subjects

Subjects enrolled in this trial will receive the new recombinant, adjuvanted varicella zoster vaccine for free. Should our hypothesis prove true, these subjects will benefit from improved protection against shingles. There will be no financial compensation of subjects for participation in this research.

10.4. Alternatives to Participation

Participation in this study is voluntary. If a subject chooses not to participate, the vaccine could be administered outside of this clinical trial.

11. CONFIDENTIALITY OF DATA AND INFORMATION STORAGE

Study specific forms within REDCap will be used for web-based data management. Information abstracted from patient care records is obtained for research purposes only. Procedures are in place for maintaining confidentiality of all information collected as part of this study. Access to medical records and the REDCap study database is limited to the investigative staff. Data are managed by study number and will be analyzed anonymously. All reports are of a summary nature and no individual patients are identified. Non-computerized medical records are kept in a locked filing cabinet. Access to personal identifiers is based on a “need to know” basis, and this access is reviewed and documented by the PI.

11.1. Investigator record Retention

The investigator shall retain study drug disposition records and all source documentation (such as laboratory reports, inpatient or office patient records) for the maximum period required by the country and Institution in which the study will be conducted. If the investigator withdraws from the study (due to relocation, retirement, etc.), the records shall be transferred.

12. RESEARCH INFORMATION IN MEDICAL RECORDS

The patient’s chart will mention that the vaccine was administered and may reference participation in the research study. The results from this study will not be reported in the patient’s chart.

13. DATA ANALYSIS AND MONITORING

13.1. Sample Size Determination

The primary endpoint for assessing the immunological response to the vaccine has been defined in section 5.2. The target accrual will be 30 evaluable subjects receiving treatment with BTK inhibitor. Allowing for 10% drop-out due to subject participation or lab testing issues, this trial will accrue a total of 33 CLL or WM patients. Based on current estimates, the expected time to accrue these subjects is 6 months.

We expect that the response to vaccine will be significantly less than the 97% response rate seen in the healthy general population. The table below shows the exact Clopper-Pearson two-sided 90% confidence intervals for a range of likely observed response rates for a range of sample sizes. The upper bound of the 90% (two-sided) confidence interval corresponds to a (one-sided) 95% confidence interval. Therefore, with 30 evaluable subjects and observed response rate

<85%, we will have 95% confidence that the true immunological response rate is less than the general population response rate.

Table 3: Two-sided 90% Confidence Intervals for a range of potential response rates by sample size

Immunologic Response Rate (%)	Sample Size		
	20	25	30
25	10 – 46%	12 – 43%	13 – 41%
35	18 – 56%	19 – 53%	21 – 52%
45	26 – 65%	28 – 63%	29 – 61%
55	35 – 74%	37 – 72%	39 – 71%
65	44 – 82%	47 – 81%	48 – 79%
75	54 – 90%	57 – 88%	59 – 87%
85	66 – 96%	68 – 95%	70 – 94%

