3. CHARACTERISTICS OF THE RESEARCH POPULATION

3.1. Subject Characteristics

a) Number of Subjects:

Target accrual is 30 evaluable CLL or WM subjects receiving treatment with BTK inhibitors. Assuming a 10% drop out rate, we aim to enroll a total of 33 subjects. Participants will be replaced in case of drop out or failure to receive the second dose of the vaccine. Failure to have blood drawn for baseline and/or 4 weeks after vaccination will also warrant replacement.

Subjects will not be replaced if they fail to present to the blood draw 24 months post-vaccination.

In the case of a change of therapy between the first and second dose of the vaccine (including the addition of rituximab), patients will remain on study and will not be replaced. Their data will be included in the estimates of vaccine response in the intent-to-treat analysis but excluded from sub-group analyses.

Based on data from the University of Rochester Cancer Center pharmacy, as of May 2018, 150 CLL and WM patients are on BTK inhibitor therapy and there are approximately 20 new cases per month. A local CLL database confirms those numbers and shows that a total of about 50 patients are on single-agent, first-line ibrutinib as of January 2018. No patient was identified while collecting this data, with respect to patients' confidentiality.

Patients who have started BTK inhibitors come to clinic about every 3 months for routine visits. Based on those numbers, we expect the recruitment of 33 patients to be feasible within 6 months.

b) Gender and Age of Subjects:

Subjects must be at least 50 years old to participate. Patients under 50 years old are excluded as per the label of the vaccine. It is anticipated that most subjects will be in their sixth or seventh decade given the age distribution of CLL²³ and WM.²⁴ There is no upper age limit if the patient meets the other inclusion criteria.

We expect that only a minority of subjects will be diagnosed with WM as compared to CLL because it is a much rarer disease, with only 1400 new cases diagnosed each year in the United States.^{25,26}

All genders are accepted. It is expected that there will be slightly more males than females included in the study as the male-to-female ratio in CLL is normally 1.3-1.7.²⁷ and about 60% of WM patients are males.²⁴

c) Racial and Ethnic Origin:

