13.2. Planned Statistical Analysis

13.2.a Primary Analysis

The estimates of geometric mean antibody titers pre- and post-vaccination, mean fold-changes, and vaccine response rates will be described with 90% (two-sided) confidence intervals. These estimates will be important for designing a future vaccine trial in patients treated with BTK inhibitors with emergence of shingles as the primary outcome. Self-reported and chart-reviewed serious adverse events will be summarized in tabular format by type and grade.

13.2.b Secondary and Exploratory Analyses

As secondary analyses, the change in antibody titers pre and post-vaccination will be evaluated with the Wilcoxon Rank Signed Test for paired data. This test will provide some indication whether the within subject change in titer is statistically different from zero. The change in seroprotection rates pre and post vaccination will be assessed by the exact McNemar test for paired proportions.

As exploratory analyses, the association between baseline characteristics and the achievement of immunological response and change in antibody titers will be assessed using exact non-parametric statistical tests, such as exact Chi-Square test, Wilcoxon Rank Sum test, or Spearman rank correlation tests, depending on the scale of the variables involved. Baseline characteristics of particular interest have been described above and include age, stage at diagnosis, time since diagnosis, presence of high-risk or low-risk features, time since BTK inhibitor therapy initiation, history of zoster reactivation, IgG levels at study entry and use of rituximab therapy. These results will be reported along with descriptive statistics for the purpose of hypothesis generation in future trials.

The disease progression to BTK inhibitor at visit 4 and visit 5 will be determined from the closest assessment by treating oncologist. The association between vaccine response and disease progression at each time point will be assessed with Fisher's exact test.

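### Is the 85% condition in section 13.1 wrong because Table 3 was computed at fractions of a patient?

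*Combined protocol and SAP*

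**What the plan says.** Section 13.1 sets the size of the trial: "The target accrual will be 30 evaluable subjects receiving treatment with BTK inhibitor". It gives the external reference: "We expect that the response to vaccine will be significantly less than the 97% response rate seen in the healthy general population". It then introduces Table 3: "The table below shows the exact Clopper-Pearson two-sided 90% confidence intervals for a range of likely observed response rates". The table lists rates from 25% to 85% in steps of 10 points, for 20, 25 and 30 subjects. The link to a one-sided statement is explicit: "The upper bound of the 90% (two-sided) confidence interval corresponds to a (one-sided) 95% confidence interval". From this the section concludes that, with 30 evaluable subjects and an observed rate "<85%, we will have 95% confidence that the true immunological response rate is less than the general population response rate".

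The primary analysis in section 13.2.a is descriptive: "vaccine response rates will be described with 90% (two-sided) confidence intervals". It names no hypothesis test, success criterion or go/no-go step. Section 3.1 adds, on top of the 10% allowance, "Participants will be replaced in case of drop out or failure to receive the second dose of the vaccine".

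**The concern.** An exact binomial interval belongs to a whole number of responders. The Table 3 rates correspond to 7.5, 10.5, 13.5, 16.5, 19.5, 22.5 and 25.5 responders out of 30, and to 6.25 up to 21.25 out of 25. So 14 of the 21 intervals described as exact cannot arise from any data set, including the whole column for the planned size. The 85% figure is the table's last row, so the cut-off seems to have been read off 25.5/30.

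This is the only inferential statement offered in support of 30 subjects. If it acted as a decision rule, a result of 26/30 would fail it although the plan's own interval excludes 97%, and the chance of meeting the criterion would be understated. Replacing drop-outs after already adding 10% also means that the evaluable number could differ from 30, and the exact cut-off shifts with that number.

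**Working it through.** **Inputs.** 30 evaluable subjects, a reference rate of 97% treated as a known constant, and the exact Clopper-Pearson two-sided 90% interval (all from section 13.1).

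**Formulas.** For x responders among n: lower limit = 5th percentile of Beta(x, n − x + 1); upper limit = 95th percentile of Beta(x + 1, n − x). The upper limit is below 97% when P(X ≤ x | n, 0.97) < 0.05.

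**Step 1: reproduce Table 3.** With x = rate × n left unrounded, all 21 printed cells are recovered. For the 85% row at n = 30, x = 25.5 gives 70.05–94.28%, printed as 70–94%. The 20-subject column uses whole counts and is exact. In the other two columns no cell matches either neighbouring whole count.

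**Step 2: whole patients at n = 30.**

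| Responders | Rate | 90% interval | P(X ≤ x at 97%) | Excludes 97%? |
|---|---|---|---|---|
| 25 | 83.3% | 68.1–93.2% | 0.0018 | yes |
| 26 | 86.7% | 72.0–95.3% | 0.0119 | yes |
| 27 | 90.0% | 76.1–97.2% | 0.0601 | no |

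The largest qualifying count is 26. A rate below 85% means 25 or fewer, all of which qualify.

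**Step 3: does the printed condition ever mislead?** It would do so only if some rate below 85% failed to exclude 97%. For each n from 20 to 35, take the largest count below 85% and compute its upper limit. The highest is 94.6%, at 22/26. At 33 subjects it is 28/33, with 93.8%. The condition therefore holds at every evaluable number the trial could plausibly reach. The exact cut-off does vary with n: 24/27, 24/28, 26/30, 29/33.

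**Step 4: how far do the Table 3 limits move?** At n = 30, going from the half-patient to either neighbouring whole count shifts a limit by 1.0 to 2.0 points. The largest shift is the lower limit of the 85% row: 70.05% against 72.04% at 26/30, a difference of 1.99. Interval widths at n = 30 change by at most about 1 point (24.2 at 25.5/30, 25.1 at 25/30, 23.3 at 26/30).

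**Step 5: what a pass/fail reading would cost.** The true rates below are assumptions.

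| True rate | P(25 or fewer) | P(26 or fewer) |
|---|---|---|
| 70% | 97.0% | 99.1% |
| 80% | 74.5% | 87.7% |
| 85% | 47.6% | 67.8% |
| 90% | 17.5% | 35.3% |

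These differences are real only if the condition is applied as a rule. Under section 13.2.a the interval itself is reported, so 26/30 appears as 72–95% and excludes 97% regardless of the 85% sentence.

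**The case for a change.** The best argument for a change is that a sample-size section should be right for the planned size and that the correction costs almost nothing: one table re-run at whole counts and one sentence edited. If 26/30 were observed, a reader could point to section 13.1 and say the claim was not covered, while the reported interval says otherwise. It is better to settle that before the data are seen. At a true rate of 85% the two readings differ by 67.8 − 47.6 = 20.2 percentage points in the chance of meeting the condition, and the 26-or-fewer version keeps its error at 0.012, well under 0.05.

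The arithmetic in this stands. The ambiguity does not, because section 13.1 says what follows from a rate under 85% and says nothing about rates above it. Nor does the 95% confidence become wrong because 25/30 happens to exclude 97% by a wide margin (a tail probability of 0.0018). The 95% is the level of the bound, and it remains so. Variation in the evaluable number does not help the argument either: the sentence is conditional on 30, and Step 3 shows that the 85% condition holds at other sizes too, whereas a fixed count of 26 is tied to 30.

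**Conclusion.** The observation is correct but calls for no change. The 25- and 30-subject columns of Table 3 are interpolations that illustrate precision at round percentages, and their 30-subject limits lie within 2 points of the attainable ones. The 85% statement is valid and slightly conservative: it leaves out one count, 26/30, that also excludes 97%. Since the primary analysis reports the interval and makes no decision at 85%, that count would still be presented and interpreted correctly. Enrolment of 33, the target of 30, the primary analysis and any conclusion about 97% are the same either way. Tabulating whole counts would be an optional editorial tidy-up.

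This rests on three things: the 97% rate is taken as fixed, as the plan takes it; the analysis stays descriptive, as section 13.2.a has it; and the evaluable number falls between 20 and 35. That the 85% figure came from the 25.5/30 row is an inference from its position in the table, and the conclusion does not depend on it.

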13.2. Planned Statistical Analysis

13.2.a Primary Analysis

The estimates of geometric mean antibody titers pre- and post-vaccination, mean fold-changes, and vaccine response rates will be described with 90% (two-sided) confidence intervals. These estimates will be important for designing a future vaccine trial in patients treated with BTK inhibitors with emergence of shingles as the primary outcome. Self-reported and chart-reviewed serious adverse events will be summarized in tabular format by type and grade.

13.2.b Secondary and Exploratory Analyses

As secondary analyses, the change in antibody titers pre and post-vaccination will be evaluated with the Wilcoxon Rank Signed Test for paired data. This test will provide some indication whether the within subject change in titer is statistically different from zero. The change in seroprotection rates pre and post vaccination will be assessed by the exact McNemar test for paired proportions.

As exploratory analyses, the association between baseline characteristics and the achievement of immunological response and change in antibody titers will be assessed using exact non-parametric statistical tests, such as exact Chi-Square test, Wilcoxon Rank Sum test, or Spearman rank correlation tests, depending on the scale of the variables involved. Baseline characteristics of particular interest have been described above and include age, stage at diagnosis, time since diagnosis, presence of high-risk or low-risk features, time since BTK inhibitor therapy initiation, history of zoster reactivation, IgG levels at study entry and use of rituximab therapy. These results will be reported along with descriptive statistics for the purpose of hypothesis generation in future trials.

The disease progression to BTK inhibitor at visit 4 and visit 5 will be determined from the closest assessment by treating oncologist. The association between vaccine response and disease progression at each time point will be assessed with Fisher's exact test.

Immunologic markers of immune response (anti-gE and cellular-mediated immunity markers) will be measured at three time points: baseline (before first vaccine dose), midpoint (4 weeks post-second vaccine dose), and endpoint (24 months post-second vaccine dose). A linear mixed model will be used to describe the change in immunologic markers over time, controlling for important baseline characteristics and including the subject as a random effect. Some markers may require transformation to approximate a normal distribution. This model will provide estimates for the shape of the effect of vaccination on these markers over the 24- month study interval, as well as inter versus intra-subject variation which will be important in the design of future trials.

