5. METHODS AND STUDY PROCEDURES

Screening procedures will take place after subjects have consented to study participation.

Subjects will be asked to return to the clinic at a later date to have the baseline blood tests performed and the vaccine administered. We will determine a selection of dates where a certain number of patients will be able to have both procedures performed on the same day.

Blood may also be drawn for baseline testing at the Cancer Center and subjects subsequently administered the vaccine at the outpatient pharmacy on screening day.

After consent, a brief chart and CLL database review will be performed to collect certain variables such as those listed below:

- Age
- Stage at diagnosis
- Date of diagnosis
- 17p deletion (yes/no)
- TP53 mutation (yes/no)
- Mutated status of IVHG (yes/no)
- 11q del (yes/no)
- Presence of trisomy 12 (yes/no)
- Del 13q (yes/no)
- Watch and wait period duration
- Date of BTK inhibitor therapy initiation
- History of zoster reactivation

- History of zoster vaccination
- Immunoglobulin levels before study start
- Use of rituximab in the past (yes/no)
 - Number of cycles
 - Date of last cycle

Prior to the first dose of the vaccine, blood will be collected to assess immunity via measurement of anti-gE and cellular-mediated immunity. Samples will be processed in the cancer center research laboratory. Peripheral blood mononuclear cells (PBMC) will be processed and cryopreserved for future cellular assays and serum will be banked for analysis of anti-gE.

At visit 2, four weeks post-first dose, subjects will be contacted by phone call to report any adverse events. A chart review for severe adverse events will also be performed.

As per the label of the vaccine, the second dose of the vaccine will be administered two months after the first one, at visit 3. One month subsequent to that second dose, at visit 4, a second blood draw will be performed to evaluate the subject's immunogenic response. The initial analyses will be repeated, and response will be measured using statistical methods described below. Safety will be assessed again in the same way as after the first dose. A chart review will be performed to assess CLL/WM progression on BTK inhibitor therapy as determined by subjects' regular team of providers during their latest visit.

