5.2. Efficacy Assessments

Vaccine response, as determined by blood antibody levels to the varicella virus glycoprotein E subunit (anti-gE), will be measured by ELISA. This humoral response will be assessed four weeks after vaccination is complete. In patients who were seropositive before the study, a positive response will be defined as at least a four-fold increase in geometric mean concentration (GMC) of anti-VZV gE antibody as measured per ELISA. Humoral response in seronegative patients at baseline will be defined as at least a four-fold increase from the lower detection limit of the anti-gE antibody assay.

Secondary efficacy objectives include:

1. Measure humoral response at 24 months post-vaccination, which is defined as persistence of anti-gE antibody above test threshold at 24 months.
2. Measure cell-mediated response to vaccination at one month and 24 months after vaccination.
3. Evaluation of CLL/WM progression on BTK inhibitor as determined by treating oncologist at latest assessment, and correlation between progression on BTK inhibitor and vaccine response at 4 weeks and at 24 months post-second dose.

Cellular-mediated response will be determined by measuring PBMC activation (by ELISPOT or flow cytometry) following stimulation with varicella glycoprotein E peptide. PBMC activation at 4 weeks and 24 months post dose will be compared to pre-vaccination activation levels.

a. Safety Assessments

Subjects will be educated to recognize immediate adverse reactions to the vaccine. Patient-reported signs of allergic or hypersensitivity reactions will be assessed and managed by the study team as needed. Only severe adverse effects will be captured in this study. Subjects will be contacted 4 weeks \pm 1 week after each dose of the vaccine for assessment and their chart will be reviewed at the same moment. Severe adverse effects are defined as any grades 3-5 adverse effects included in the CTCAE v5.0 classification.

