The decision was made not to report all side effects because the safety of this vaccine has already been proven in large clinical trials, both in a general population of older adults and in immunocompromised patients, including lymphoma patients receiving chemotherapy. These thousands of patients did not experience significant toxicity from herpes zoster vaccination.^{3,13} Moreover, clinically relevant concerns to vaccine administration are grade 3-5 toxicities, which will be captured in the study, both via patient-reported toxicity and through chart review.

b. Assessment of Subject Compliance

All study procedures (vaccine administration and blood draws) will be performed at Strong Memorial Hospital, which will ensure compliance.

c. Costs to the Subject

Cost and administration of the vaccine and all required laboratory testing is covered by the study. Collection and maintenance of research records, laboratory assays and storage of blood samples will also be covered by the study. There will be no direct cost to the subjects to be part of the research project.

d. Payment for Participation

Subjects will not receive payments for their participation in the study.

e. Return of Individual Research Results

Patients will not directly be notified of the results as there will be no direct clinical implications to the observed immunological response. However, that information will be made available through their hematologist after the study is finished.

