7. SUBJECT WITHDRAWALS

Subjects will be advised in the written informed consent forms that they have the right to withdraw from the study at any time without prejudice. Withdrawal of consent can be submitted to any member of the research team, after which point no further data will be collected on these patients.

Subjects may be withdrawn by the investigator if they fail to present for the second dose of the vaccine or for the first control blood draws, or if they experience a severe adverse effect attributed to the first dose of the vaccine.

If therapy needs to be modified and subjects stop BTK inhibitor therapy between enrollment and their second vaccine dose, they will be offered the second dose and remain on study.

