8.2. Dosage of Study Drug/Biologic

Dosage of study drug: Shingrix vaccine 50 mcg of anti-gE protein and adjuvant product given at month 0 and month 2.

Should a vaccine-related SAE happen between doses 1 and 2, dose 2 may be omitted. There will be no other dose adjustment.

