9. SAFETY AND REPORTABLE EVENTS

9.1. Serious Adverse Event

A serious adverse event is defined as any adverse medical experience that results in any of the following outcomes:

- death;
- is life-threatening;
- requires inpatient hospitalization or prolongation of existing hospitalization;
- results in persistent or significant disability/incapacity;
- is a congenital anomaly/birth defect; or
- requires medical or surgical intervention to prevent permanent impairment or damage.

The following attribution scale will be used:

- Definite: SAE is clearly related to the investigational agent
- Probable: SAE is likely related to the investigational agent
- Possible: SAE is possibly related to the investigational agent
- Unlikely: SAE is doubtfully related to the investigational agent
- Unrelated: SAE is clearly not related to the investigational agent

Serious adverse events, and deaths that occur during the patient's study participation will be recorded in the REDCap database. SAEs will be monitored from the first dose of study vaccine until 4 weeks (28 days) post-last dose of vaccine or withdrawal from participation. All SAEs should be monitored until they are resolved or are clearly determined to be due to a patient's stable or chronic condition or intercurrent illness(es).

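### The only planned safety table covers *serious* events, while the post-dose assessment captures *severe* (grade 3–5) events; as written, non-serious grade 3–5 events would not be tabulated

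*Combined protocol and SAP*

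**What the plan says.** Three parts of the combined protocol and SAP bear on this point.

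- **Capture after each dose.** Section 5 describes a phone contact four weeks after dose 1 and adds: "A chart review for severe adverse events will also be performed". Safety is assessed in the same way after dose 2. Section 5.2, item a (Safety Assessments), states: "Only severe adverse effects will be captured in this study". It then defines the term: "Severe adverse effects are defined as any grades 3-5 adverse effects included in the CTCAE v5.0 classification". The reason given for not reporting every side effect is that "clinically relevant concerns to vaccine administration are grade 3-5 toxicities, which will be captured in the study", with patient report and chart review as the two sources.
- **Serious events.** Section 9.1 opens its definition with "A serious adverse event is defined as any adverse medical experience that results in any of the following outcomes" and lists death, threat to life, hospitalization, disability, congenital anomaly, and intervention to prevent permanent damage. It sets no grade threshold. These events are monitored from dose 1 until 28 days after the last dose. Section 9.2 requires all of them to be entered in REDCap within 5 business days, with the toxicity grade.
- **Analysis.** Section 13.2.a has one safety sentence: "Self-reported and chart-reviewed serious adverse events will be summarized in tabular format by type and grade". Nothing else in Section 13.2 summarizes adverse events.

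**The concern.** The protocol gives *severe* and *serious* different meanings, one based on grade and the other on outcome. The word used in 13.2.a therefore decides which events reach the table. The post-dose assessment is built around the first term and the table around the second.

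What is at stake is how the safety results can be read. The protocol drops lower-grade events on the ground that grade 3–5 toxicities are what matters clinically and will be captured. If the table then leaves out the grade 3–5 events that are not serious, a reader cannot tell whether none occurred or whether they were simply not tabulated. Section 10.1 lists local and systemic reactions such as injection-site pain (78.0%), myalgia (44.7%) and fatigue (44.5%). These figures are not broken down by grade, so they say nothing about how many events would be affected. They do show the kind of event that could be graded severe without meeting any Section 9.1 outcome.

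**Working it through.** No formula applies and the plan states no figure to reproduce. The check is to cross grade with seriousness, using the protocol's own definitions, and follow each group from capture to table.

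| Event group | Recorded under | In the 13.2.a table as written (*serious*) | If *severe* was meant |
|---|---|---|---|
| Grade 3–5, serious | 5.2 and 9.1–9.2 | Yes | Yes |
| Grade 3–5, not serious | 5.2 | **No** | Yes |
| Grade 1–2, serious | 9.1–9.2 | Yes | **No** |
| Grade 1–2, not serious | Not captured (5.2) | No | No |

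1. The second row is the gap. Section 5.2 captures these events, no Section 9.1 outcome makes them serious, and no sentence in 13.2.a or 13.2.b summarizes them.
2. The third row depends on how two sections are reconciled. Section 5.2, read literally, captures only severe effects, which would exclude a grade 1–2 serious event. Sections 9.1 and 9.2 record all serious events without regard to grade. I have let the latter govern because they are specific to serious events, but the text does not settle it.
3. Replacing *serious* with *severe* in 13.2.a would close the second row and open the third. A one-word swap is therefore not a complete repair.
4. The reference to grade in 13.2.a does not show which word was meant, because Section 9.2 asks for the toxicity grade of serious events too.
5. Section 13.3 does not fill the gap. Its progress reports to the monitoring committee include significant toxicities alongside serious events, but these reports are oversight rather than a planned analysis, and the protocol does not define which toxicities count as significant.

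The rows are categories, not counts. They show which events the wording leaves out, not how many there would be.

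**The case against.** The strongest reply is that this is a wording slip with an evident intent. Section 5.2 names patient report and chart review as the sources for grade 3–5 toxicities, and 13.2.a names the same two sources. Section 13.3 also describes some serious events by toxicity grades 3 to 5, so the authors do not keep the terms apart. On that reading, the non-serious grade 3–5 events were always meant to be tabulated. The data are collected either way, safety is not a stated primary or secondary objective, and the table could be put right at reporting.

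Most of this stands: a slip is the likelier explanation, and no data are lost. It does not remove the point. *Serious* is a defined term here, an analyst following 13.2.a literally would produce an incomplete table, and simple substitution leaves its own omission.

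A reader might infer more than the documents support:

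- *That the study records only severe events.* Sections 9.1 and 9.2 also record serious ones.
- *That a known share of events would be missed.* No rate is given for non-serious grade 3–5 events or for grade 1–2 serious events.
- *That events in withdrawn or replaced subjects would be dropped.* No text limits the table to evaluable subjects.
- *That the withdrawal and second-dose provisions prove the terms are interchangeable.* Section 7 allows withdrawal of subjects "if they experience a severe adverse effect attributed to the first dose of the vaccine", and Section 8.2 says "Should a vaccine-related SAE happen between doses 1 and 2, dose 2 may be omitted". These are two different permissive actions, and they are not needed to establish the gap. No position is taken on which term should govern them.

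**Conclusion.** The point holds as a mismatch between capture and analysis. Taken as written, 13.2.a omits captured grade 3–5 events that meet no Section 9.1 outcome from the only planned safety summary, although Section 5.2 presents grade 3–5 toxicity as the clinically relevant concern. The number of events affected is unknown and may be nil. The response-rate estimate, its confidence interval and the sample size are untouched.

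The conclusion assumes that the two terms carry the definitions in Sections 5.2 and 9.1 wherever they appear, and that the progress reports in Section 13.3 are not a substitute for the planned table. If the authors meant *severe*, the intended table would cover the gap but the text still needs correcting, and grade 1–2 serious events would need to be provided for. The change should be made, since it is cheap and makes the safety table interpretable.

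**What to change.** Replace the safety sentence in 13.2.a with wording such as: *All captured grade 3–5 adverse events, and all serious adverse events (Section 9.1) of any grade, will be tabulated by type and grade, with serious events flagged.*

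Then align the terms:

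- Use *severe* for grade and *serious* for outcome throughout Sections 5, 5.2, 9.1, 13.2.a and 13.3.
- Reconcile the statement in Section 5.2 that only severe effects are captured with the recording of all serious events in Sections 9.1 and 9.2.

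An optional clarification is to state that the table covers all subjects given at least one dose. If this is added, note that follow-up can differ between subjects, because data collection stops when consent is withdrawn (Section 7) and monitoring of serious events ends at withdrawal from participation (Section 9.1).

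The cost is one sentence and some editing, slightly more tabulation, and a safety table that may look less favourable. No new data collection is required.
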